The prognosis of a ureteral stone as can be conveyed to the patient is based on a historical study from Miller and Kane. In 1999, the authors studied 75 patients with ureteral stones ranging from less than 2mm to 10mm over approximately 6 weeks' time. It was found that smaller, more distal stones pass sooner and that stones <4mm pass 95% of the time, although this may take up to 40 days [13]. Since that time, multiple studies have shown medical expulsive therapy (MET) to be effective for earlier stone passage [14, 15, 16]. No modern investigation of stone passage rates based on size has been performed in the MET era.

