3.0 PATIENT SELECTION

3.1 Inclusion Criteria

Patients must meet all of the following inclusion criteria to be eligible for study participation:

1. Age 18 and older at the time of consent
2. Willing and able to sign consent
3. CT diagnosis of ureteral stone with a stone burden less than or equal to 10mm

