5.2 Study Plan and Procedures

Study RBUS with UJA will be obtained within 10 days following CT diagnosis of ureteral calculus. Ureteral jet data will be documented and patients will be followed prospectively for 42 days at 2 weeks, 4 weeks and 42 days (6 weeks) after diagnostic CT. Specifically, patients will be followed for spontaneous stone passage and will be expected to record date of stone retrieval. If specific date of stone passage is not known, date of standard of care imaging confirming absence of stone(s) will be used as the date of stone passage. If spontaneous stone passage is not achieved, patients will be counseled regarding further standard of care treatment options including surgical stone removal. If surgical intervention is indicated, time to surgical procedure will also be recorded. This patient cohort will be analyzed retrospectively to determine whether RBUS with UJA is predictive of spontaneous stone passage versus need for surgical intervention over a 42-day period.

Interpretation of RBUS and UJA:

Abdominal radiologists will interpret the RBUS research reads. All grey scale and color Doppler examinations will be performed by means of a commercially available unit with a 1-5 MHz phased array transducer or a 1-6 curved transducer. Flow toward the transducer is assigned a red color on Doppler. For grey scale evaluation, the presence or absence of urinary tract stones, size (longest axis in mm) and location- R, L, upper pole, interpolar and lower pole of the kidneys, proximal ureter, distal ureter and bladder- will be documented. The level of the renal pelvis represents the interpolar kidney with upper and lower pole above and below this level. For this study, a urinary tract stone will be termed an echogenic focus that demonstrates either posterior acoustic shadowing and or twinkle artifact on color Doppler images. In addition, presence of hydronephrosis (mild, moderate, and severe) will be documented. For the purpose of this read, hydronephrosis will be defined as such: mild hydronephrosis - urine fills the intra and extra renal pelvis and the major calyces are dilated; moderate hydronephrosis – above + dilatation of the minor calyx with preservation of the renal parenchyma; severe hydronephrosis – above +

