thin renal parenchyma. In addition, the presence or absence of hydroureter (proximal ureter, above the iliac bifurcation and distal ureter, below the iliac bifurcation) will be documented. If there is a stone in the renal pelvis, it will be recorded as interpolar kidney and noted as renal pelvis. For any case, if the reader believes that a particular stone is the cause of the participant's symptoms, then this will be noted. This is particularly useful in cases in which there are multiple stones. The bladder will be examined in the transverse plane at the level of the trigone to view both jets simultaneously. All participants will be scanned for 5 minutes. The number of jets from each ureteral orifice will be tabulated over time so that ureteral jet frequency, defined as number of jets per minute, can be calculated. Patients will be categorized into three groups. Group I- no ureteral jets on the symptomatic side; Group II- continuous low-level ureteral jet on the symptomatic side; Group III- ureteral jets similar to nonsymptomatic side.

In order to determine if RBUS with UJA along with clinical data confers non-inferior information compared to non-contrast CT, objective findings such as laboratory data including BMP, CBC, urine analysis and physical exam obtained as part of routine care will be retrieved from the patient's medical record and reviewed retrospectively. Clinical data and RBUS results will be de-identified/coded and the Urologist will be blinded to the CT results. Diagnosis and treatment recommendations will be determined based upon these findings and compared to those attained by CT to assess for congruence. Statistical analysis will be performed to determine non-inferiority between the studies.

Stone size and location based on CT will be recorded at the time of enrollment into the study and time to stone passage will be recorded. All study participants will be followed for stone passage. Time to stone passage will be stratified according to stone location (proximal, mid or distal ureter) and size (<2mm, 2-4mm, 5mm, 6-7mm, 9-10mm).

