7.0 STATISTICAL CONSIDERATIONS

7.1 Study Objectives and Endpoints

Primary Outcome:

To determine if RBUS with UJA is prognostic of stone passage versus need for

surgical intervention:

1. Passage of stone as assessed by patient self-report and/or collection of stone or imaging.
2. Need for further medical attention as collected by chart review and phone interview for ED visit, hospitalization, or need for surgical intervention during the 42-day follow-up period.

Secondary Outcomes:

1. To determine if RBUS with UJA, in conjunction with standard of care laboratory data and history and physical confers non-inferior information compared to non-contrasted CT:
 - a. Urologist will review the patient's de-identified/coded history and physical, laboratory studies, and RBUS with UJA and make an assessment and treatment recommendations. The urologist will be blinded to the results of the CT. Comparison will be made between the CT diagnosis and the blinded assessment of the urologist.
2. To determine if the natural history and rate and time of stone passage for ureteral stones of differing locations (proximal, mid or distal ureter) and sizes (<2mm, 2-4mm, 5mm, 6-7mm, 9-10mm):
 - a. Assessment of the stone location and size to be conducted by a radiologist.

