7.3 Data Analysis

Primary objective:

This patient cohort will be analyzed retrospectively to determine whether US with UJA is predictive of spontaneous stone passage versus need for surgical intervention. Kaplan-Meier curve will be used to test time to spontaneous stone passage between the two groups. A chi-square test of independence will be used to test intervention rates between the two groups. A multivariate analysis will also be conducted controlling for such variables as age, gender, BMI, side, size of stone, and stone passage. A Cox-proportional hazards model will be used for time to spontaneous stone passage and logistic regression will be used for intervention.

Due to the unforeseen difficulty of recruitment and the uncertain assumptions of the initial power analysis, an interim statistical analysis is recommended to be performed when the recruitment reaches 50 patients. Based on the results, a decision will be made whether to continue recruitment to the initial 100 targeted patients, adjust the number of targeted patients based on a new power analysis, or to discontinue recruitment. The interim results

should not affect primary independent variables in the study as the radiologist performing the ultrasounds will not have access to the results.

Secondary objective 1:

Statistical analysis will be performed to determine diagnostic and treatment concordance between the two methods. A multivariate logistic regression model will also test patient factors that are associated with discordant results.

Secondary objective 2:

In a prospective manner, they will be followed to determine the natural history of ureteral stones with regard to stone passage. Average time to stone passage for each size category and stone location will be determined. Cox-proportional hazard models will be used to determine significant factors affecting time to stone passage.

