APPENDIX A: Study Schedule of Events

		Post-Enrollment Assessment and Follow-up		
		Within one day of diagnostic CT	2 weeks post diagnostic CT (+/- 2 days)	4 weeks post diagnostic CT (+/- 2 days)
Informed Consent	X			
Incl./Excl. Criteria Confirmation	X			
RBUS with UJA	X			
Demographics¹	X			
Medical & Surgical History¹	X			
Height & Weight¹	X			
Basic metabolic panel¹	X			
Complete blood count¹	X			
Urine analysis and microscopy¹	X			
CT scan¹	X			
Assessments:				
Study related AEs/reportable events		X	X	X
Clinical stone management¹		X	X	X
Passage of stone		X	X	X

¹ as part of standard clinical care.

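### Secondary objective 1 compares RBUS with a CT up to 10 days older and has no rule for stones that pass or change in between, so real change may be counted as disagreement between the methods

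*Combined protocol and SAP*

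**What the plan says.** On timing, Section 5.2 reads: "Study RBUS with UJA will be obtained within 10 days following CT diagnosis of ureteral calculus". Appendix A has a column headed "Within one day of diagnostic CT", and the baseline items, RBUS among them, appear to belong to it. The table is broken in the text available, so that placement is not certain.

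On the comparison, Section 5.2 says of the RBUS and clinical findings: "Diagnosis and treatment recommendations will be determined based upon these findings and compared to those attained by CT to assess for congruence". Section 7.1 names the reference: "Comparison will be made between the CT diagnosis and the blinded assessment of the urologist". The urologist works from coded history, examination, laboratory results and RBUS with UJA, blinded to CT.

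On the population, Section 3.1 requires "CT diagnosis of ureteral stone with a stone burden less than or equal to 10mm".

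On the analysis, Section 7.3 says: "Statistical analysis will be performed to determine diagnostic and treatment concordance between the two methods". It adds a logistic model for patient factors associated with discordance. Section 5.2 also promises a non-inferiority assessment, for which no margin is given.

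On natural history, Section 1.1 says that smaller and more distal stones pass sooner. It gives one rate: "stones <4mm pass 95% of the time, although this may take up to 40 days".

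**The concern.** A comparison of two imaging methods needs both to look at the same disease state. Here the reference is fixed at presentation, and the index scan may follow by as much as 10 days in a condition that can resolve on its own. A technically correct RBUS may show no stone because the stone has gone, or less hydronephrosis because the obstruction has eased. Set against the earlier CT, that can look like an RBUS miss.

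The delay is realistic. Section 1.2 recruits from the Urology office as well as the ED. Section 5.1 allows contact by phone and consent forms sent home, with a face-to-face discussion and signature still required before any study procedure.

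Two results are at stake. One is the concordance estimate, which would mix RBUS performance with the course of the disease. The other is the discordance model. Stone size and location affect how soon a stone passes. If they enter the model without the CT-to-RBUS interval, they may be reported as reasons why RBUS fails when part of the cause is elapsed time.

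**Working it through.** The plan gives no agreement figure, agreement statistic or non-inferiority margin, so there is no figure of its own to reproduce. The target of about 100 participants (Section 7.2) has no alpha, power or effect size attached, and the point does not depend on it. The check has a textual part and an illustrative calculation.

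**Text.**
1. The reference is the diagnostic CT (Section 7.1), and no repeat CT is planned at the time of the RBUS.
2. Section 3.2 does not exclude participants whose stone passes before the RBUS.
3. Section 7.3 has no restriction or adjustment for the interval, and no separate class for stones already passed.
4. Dates of passage are collected (Section 5.2) but are not used for this objective.
5. All participants are CT-positive, so on stone presence a change between scans can only go from present to absent. It can remove agreement but cannot create it.

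**Share of stones gone before the RBUS.** Let P be the proportion passed by day 40 and t the day of the scan. Two shapes are used, because the documents give no day-by-day curve:
- even spread: P × t/40
- constant hazard: 1 − (1 − P)^(t/40)

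For scans spread evenly over days 0-10, the average share is P × 5/40 under even spread. Under constant hazard it is 1 − (1 − e^(−10λ))/(10λ), with λ = −ln(1 − P)/40.

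P = 0.95 is the Section 1.1 figure for stones <4 mm, read as 95% passed by day 40. P = 0.50 and 0.70 are assumptions for a mixed cohort of stones up to 10 mm. Each cell gives even spread, then constant hazard.

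| P by day 40 | Scan on day 1 | Scan on day 10 | Scans spread over days 0-10 |
|---|---|---|---|
| 0.95 (<4 mm) | 2.4%, 7.2% | 23.8%, 52.7% | 11.9%, 29.6% |
| 0.70 (assumed) | 1.8%, 3.0% | 17.5%, 26.0% | 8.8%, 13.7% |
| 0.50 (assumed) | 1.3%, 1.7% | 12.5%, 15.9% | 6.3%, 8.2% |

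The mixed cohort with scans spread over the window therefore gives about 6-14% gone.

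**Effect on apparent agreement.** Let c be agreement had both scans been made at the same time (0.90, assumed) and g the share gone. Take passage to be unrelated to whether the RBUS would have agreed.
- All passed stones scored discordant, c(1 − g): 0.90 × 0.94 = 0.846 and 0.90 × 0.86 = 0.774, so about 77-85%.
- Half scored discordant, c(1 − g/2): 0.90 × 0.97 = 0.873 and 0.90 × 0.93 = 0.837, so about 84-87%.

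For scale, the 95% half-width at 100 participants and 90% agreement is 1.96 × √(0.90 × 0.10/100) = 0.059, about 6 points. The loss is about 5-13 points in the first case and 3-6 in the second. It may therefore fall below, match or exceed sampling error.

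**The case against.** The strongest reply is that no scoring rule is written. A reader might infer that the plan counts every passed or moved stone as a disagreement, but the documents do not say so. They describe a comparison and leave the classification open. The urologist sees history, examination and laboratory data as well as the scan, so a stone that has left may still be diagnosed correctly. Movement matters only if location is part of the diagnosis compared or changes the recommendation, and that is not stated either. All of this stands, and it limits the claim to what may be scored.

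A reader might also infer a much larger loss, with agreement falling to 0.90 × (1 − 0.30) = 63%. That needs 30% of stones gone and every one scored discordant. A share near 30% comes from the <4 mm rate under constant hazard, while the cohort includes stones up to 10 mm and Section 1.2 expects larger stones to pass less often. The documents do not support 63% as an expected result.

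If the one-day heading in Appendix A governs the RBUS, the share gone falls to about 1-3% in the mixed cohort (2-7% for stones <4 mm), and what remains is mainly a conflict of wording. The broken table does not settle this.

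The bias runs against RBUS on stone presence, so it makes non-inferiority harder to show and does not favour a false claim for RBUS. That is fair, but an estimate biased downward still misstates how well RBUS performs.

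Finally, Section 7.3 does not list stone size or location for the discordance model, so harm to that model is possible rather than certain.

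**Conclusion.** The point holds in a limited form. Following Section 5.2 as written permits a gap of up to 10 days between index and reference imaging, and nothing in the analysis separates a change in the patient from an error of the method. The direction is clear for stone presence. It is not established for location or for treatment recommendations.

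The size is illustrative only. It rests on an assumed 50-70% passage by day 40, scans spread evenly over the window, and an assumed true agreement of 90%. On that basis, apparent agreement is about 77-85% if all passed stones are scored discordant and 84-87% if half are. For stones <4 mm scanned on day 10, the share already gone is about 24-53%. The even-spread figures are not strict lower bounds, since passage could be slower at first.

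The point concerns the RBUS-CT comparison alone. It does not show that the 10-day window is wrong for the primary objective.

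**What to change.** 1. Reconcile the RBUS window in Section 5.2 with the column heading in Appendix A, so that one window is stated in both places.
2. In Section 7.3, add the CT-to-RBUS interval in days as a covariate in the discordance model. A main effect shows whether discordance rises with the gap, but it will not fully separate elapsed time from stone size or location, which act partly through passage during that gap. Item 3 is therefore also needed.
3. In Section 7.3, pre-specify a concordance analysis limited to short-interval pairs with no known passage or intervention before the RBUS, reported beside the all-participant result. Fix the interval cut-off before agreement results are seen. Making this subset the only analysis is not warranted, because the number scanned early is unknown.
4. State how a stone known to have passed before the RBUS is classified, and whether location counts in the comparison.

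The cost is wording. The CT date already anchors follow-up, and the RBUS date is needed to apply any window. The restricted set will be smaller and its intervals wider. It will not remove all of the bias. The first call is at 2 weeks, after the 10-day window has closed, and an unknown passage date is replaced by the date of confirming imaging, so some early passages may still be missed.

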1.2 Rationale

Due to the increasing use of CT and concern for radiation exposure, it is important to consider alternative diagnostic imaging modalities. We seek to evaluate patients who present to the Barnes-Jewish Hospital (BJH) ED and to the Urology office with renal colic who have been diagnosed with a ureteral stone. We seek to determine whether the findings on ureteral jet assessment (UJA) by RBUS are predictive of a patient's clinical outcome. Specifically, we seek to

evaluate whether the presence, absence or relative strength of the ipsilateral ureteral jet can predict spontaneous passage versus need for surgical intervention over a 42-day (6-week) time period. As many patients have a life-long affliction with nephrolithiasis[1], the potential for a considerable aggregate accumulation of radiation exposure over their lifespan can be excessive and should not be overlooked [5, 7, 8]. This patient population, especially those first diagnosed at a young age, would benefit from imaging modalities that do not involve radiation.

Evaluating the significance of UJA and RBUS in patients with renal colic will help define the role of this imaging modality, as an alternative to ionizing radiation-based studies. The prognosis of urolithiasis based on UJA will be defined, as well as the natural history of stones managed expectantly. We hypothesize that UJA showing weak or absent ureteral jet will predict obstruction and a higher rate of surgical treatment compared to spontaneous passage. We hypothesize that larger stones will be less likely to pass without surgical intervention.

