5.3 Study Follow-up

After study RBUS is obtained, patients will be followed prospectively by telephone call at 2 weeks, 4 weeks and 42 days (6 weeks) from the time of diagnostic CT. They will be followed for spontaneous stone passage, and be asked to keep record of when this occurs. During the 42-day follow up, their course will also be monitored for ED visits, surgical intervention and hospital admissions. All currently available medical records such as Clindesk, Allscripts, Compass, HMED will be reviewed retrospectively to follow participants' clinical course, specifically to determine the need for surgical intervention or spontaneous stone passage. Billing records may also be used to identify patients who underwent surgical intervention based on CPT codes. Evaluation of the patient's emergency room records with a focus on their presenting symptomatology and initial evaluation by the emergency provider will be performed. Any additional laboratory tests and/or imaging obtained during their emergency room or office visit will also be reviewed and collected for study purposes.

Surgical intervention, including ureteral stent or nephrostomy tube placement, ureteroscopy/laser lithotripsy, or extracorporeal shockwave lithotripsy (ESWL) will be instituted, as per standard of care. A follow up telephone call at 2 weeks, 4 weeks and 42

days (6 weeks) from the time of diagnostic CT will be performed in case of care received outside of the Barnes-Jewish Hospital (BJH) system and medical records reviewed for ER visits, hospital admissions and surgical intervention.

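### No confirmation of passage status is required at day 42, so unseen passage, if commoner for small stones, would bias the size–passage relation toward the null

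*Combined protocol and SAP*

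**What the plan says.** The endpoint in Section 7.1 is "Passage of stone as assessed by patient self-report and/or collection of stone or imaging". Section 5.2 asks the patient to supply the date: "patients will be followed for spontaneous stone passage and will be expected to record date of stone retrieval". It gives a fallback when the date is not known: "date of standard of care imaging confirming absence of stone(s) will be used as the date of stone passage". Section 5.3 has patients "followed prospectively by telephone call at 2 weeks, 4 weeks and 42 days (6 weeks) from the time of diagnostic CT", and has medical records reviewed "specifically to determine the need for surgical intervention or spontaneous stone passage". It adds that "Any additional laboratory tests and/or imaging obtained during their emergency room or office visit will also be reviewed and collected for study purposes". Section 5.5 mentions a urology clinic visit under standard of care and names no imaging.

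No section schedules a follow-up image. Appendix A marks CT and RBUS only in the baseline column; its column headings are partly lost in the available text, but nothing elsewhere contradicts it. The available text gives no instruction to strain urine, no ranking of conflicting sources, and no rule for a patient whose stone was neither seen nor imaged.

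The same endpoint is then broken down by size: "Time to stone passage will be stratified according to stone location (proximal, mid or distal ureter) and size (<2mm, 2-4mm, 5mm, 6-7mm, 9-10mm". Section 1.2 states the direction expected: "We hypothesize that larger stones will be less likely to pass without surgical intervention". Section 7.3 plans average time to passage by size and location and Cox models for secondary objective 2, and Kaplan-Meier and Cox analyses of time to passage for the primary objective.

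**The concern.** A passage enters the data only if the patient notices it, an image happens to be taken, or a record mentions it. Calls collect what the patient noticed. Records hold a passage only if somebody observed, reported or imaged it. Neither recovers a stone that left unseen. Section 7.3 has no category for unknown status, so a responder with an unseen passage and no later image or surgery counts as event-free through day 42.

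This would matter little for the size comparison if unseen passage were equally common at every size. The size bands, however, start below 2 mm, and it is reasonable to suspect that such a stone is noticed less often than one of 9–10 mm. If so, events are lost mostly where the study's own hypothesis expects most of them. Passage rates in the small bands would be too low, and the test of the larger-stone hypothesis would be biased toward no effect.

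A second route acts on time. When passage is found only by imaging, the imaging date replaces the unknown date, so time to passage is lengthened even though the event is eventually counted. If small stones rely more on imaging, this also weakens the size effect.

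**Working it through.** The plan gives no figure to reproduce here. Section 7.2 states about 100 participants, Section 7.3 calls the assumptions of the initial power analysis uncertain, and neither alpha, power, effect size nor event rate is given. What follows is an illustration.

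**Inputs**
- True passage of small stones, p = 0.95: from the historical study described in Section 1.1, for stones under 4 mm. It stands in for the <2 mm and 2–4 mm bands.
- True passage of larger stones, p = 0.55: assumed.
- 50 patients per size group: an assumed even split of the roughly 100 planned.
- d, the share of passages the patient notices: assumed 0.90 for large stones; 0.90, 0.80, 0.70 or 0.50 for small.
- m, the share of unnoticed passages caught by incidental imaging or records: assumed 0, 0.3 or 0.6.
- False-positive self-report: set to zero.

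**Formula.** Recorded passage = p × [d + (1 − d) × m].

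Large stones: 0.55 × 0.90 = 0.495 (m = 0); 0.55 × 0.93 = 0.512 (m = 0.3); 0.55 × 0.96 = 0.528 (m = 0.6).

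Small stones at d = 0.80: 0.95 × 0.80 = 0.760; 0.95 × 0.86 = 0.817; 0.95 × 0.92 = 0.874. The other rows follow in the same way.

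| Small-stone passages noticed | Recorded small-stone passage, m = 0 / 0.3 / 0.6 | Recorded gap (points) | Power |
|---|---|---|---|
| 90% (same as large) | 0.855 / 0.884 / 0.912 | 36 / 37 / 38 | 98% / 99% / 99% |
| 80% | 0.760 / 0.817 / 0.874 | 27 / 31 / 35 | 79% / 91% / 98% |
| 70% | 0.665 / 0.751 / 0.836 | 17 / 24 / 31 | 40% / 70% / 92% |
| 50% | 0.475 / 0.618 / 0.760 | −2 / 11 / 23 | about 5% / 19% / 68% |

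The true gap is 0.95 − 0.55 = 40 points, with power above 99%. Power is for a two-sided 5% comparison of two proportions, 50 against 50. Section 7.3 plans Cox models, so the power column is a guide to scale and not the power of the planned test.

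Equal detection costs only 2–4 points of the gap. The larger losses come from detection that differs by size.

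**Late dating.** A simulation with other assumptions (a large-stone passage rate of 0.50, exponential times, 5,000 per group, unnoticed passages dated by an image on days 28–42) has a true hazard ratio of ln(0.05)/ln(0.50) = 4.3. Here detection is written small/large.
- With no imaging, the recorded hazard ratio is about 2.5 at 0.80/0.95 and 1.5 at 0.60/0.95.
- With half the misses imaged, it is about 3.0 and 2.1.
- With every miss imaged, it is still only about 3.6 and 3.2, because those events carry the later imaging date.

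**Large-stone passage.** At 0.80/0.95 with no imaging, varying true large-stone passage from 0.40 to 0.70 moves the recorded gap from 38 to 9.5 points, against true gaps of 55 to 25.

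**The case against.** The strongest objection is that the decisive premise is not in the documents. Nothing there says that detection varies with stone size, and with equal detection the gap barely moves. This stands, and it is why the conclusion must be conditional. A reader might infer that small stones are in fact under-recorded in this study; the text does not support that.

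Second, a reader might infer that the plan tells the analyst to code such patients as not passed. It does not. Section 7.3 is silent, and the event-free status follows from that silence in an ordinary Kaplan-Meier or Cox analysis.

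Third, the safeguards are more than incidental imaging. Self-report counts without a retrieved stone, three calls are planned, records are searched for passage, and a clinic visit is expected. So the m = 0 column is an extreme. Still, none of these sources reveals a stone that nobody saw and nobody imaged.

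Fourth, at 80% against 90% detection the recorded gap is still 27–35 points with power of 79–98%, so a modest difference in detection need not hide the relation. This stands.

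Fifth, patients may be told how to catch the stone in consent material, which was not available for this review. The strainer part of the fix may then already be partly met; the missing status rule would not be.

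Finally, false-positive self-report is a separate error that raises recorded passage. It does not cancel this one: at 0.80/0.95 with no imaging and a large-stone passage rate of 0.50, letting 20% of unpassed stones be reported as passed shrinks the gap further, from 28.5 to 19.5 points.

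**Conclusion.** The point holds conditionally. The documents establish that passage rests on patient notice or retrieval plus incidental imaging and records, that no confirmation is required by day 42, and that an unseen, unimaged passage yields no event. If unseen passage is commoner for small stones, secondary objective 2 is biased toward the null. In the illustration the true 40-point gap is recorded anywhere from 35 points down to −2, depending on detection rates and imaging coverage that the documents do not give. Only the 95% comes from the protocol; the 55%, the even split and all detection and imaging rates are assumptions.

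A reader might also infer that the adjusted UJA effect is distorted because size is a covariate in the primary Cox model. Size is measured by CT and is not the mismeasured variable. The primary time-to-passage analysis does share the endpoint and so is exposed to missed passages, but the effect there has not been quantified. The chi-square and logistic analyses of intervention do not use passage as their outcome.

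The change should be made, because without it stones not seen and stones not passed cannot be told apart afterwards.

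**What to change.** 1. **Sections 5.2 and 5.3.** Give each participant a urine strainer at the RBUS visit, and ask at each planned call whether it was used and whether a stone was caught. Record the source of every passage determination: stone caught, self-report only, imaging, or records. If strainers start after enrolment has begun, record who received one, since detection will then differ between earlier and later participants.

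2. **Section 7.3.** Code a patient with no stone seen, no later image, no record of passage and no surgery by day 42 as passage status unknown. Report passage by size with two bounds: all unknown passed, and none passed. Repeat the size Cox model under both. The all-passed bound needs event times, so treat unknown passages as interval-censored between the last contact or image at which the stone was known to be present and day 42. Treat imaging-dated passages in the same way, with the imaging date as the upper limit; this also deals with late dating.

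The cost is a low-cost strainer per participant, two call questions and some extra sensitivity runs. The price in the results is wider limits in the small-stone bands. No imaging, visits or staff are added.
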